METHODOLOGICAL PROCEDURES & DOCUMENTS MANUAL

Reducing Maternal Depression and Promoting Infant
Social-Emotional Health & Development

NIH R01 HD086894

NCT03464630

Randomized Controlled Trial Design: Prior to iPhone set up, the Intervention Project Coordinator implements randomization procedures. Using a random number generator, mother-infant dyads were randomized, in a 1:1 allocation, to one of the two parallel interventions: Mom and Baby Net or Depression and Developmental Awareness. The Intervention Project Coordinator notifies the PI to review condition assignment and assigns case to intervention coach. (see pages 26 and 98 in Procedures below)

Objective and Specific Aims:

The objective of this project was to address the problem of silo interventions and to improve accessibility to intervention that both reduces maternal depression and improves infant social emotional and communication development. To achieve this objective the following specific aims were addressed:

1. Embed core components of the Mom-Net Internet intervention into the Internet based virtual coaching intervention, Baby Net, to create Mom and Baby Net, an instructionally sound program geared to reduce the internal demands of depressed mothers postpartum.
2. Evaluate the impact of the Mom and Baby Net (MBN) program, as compared to a parallel Internet remote coaching intervention: Depression and Developmental Awareness (DDAS), via a randomized controlled trial. Depressed mothers during the postpartum period and their infants (N=180 dyads) will be randomized to the MBN or DDAS . Impact will be examined relative to:
 - 2.1 Change in parenting behavior, attitudes, beliefs, knowledge, and stress;
 - 2.2 Infant social-emotional behavior and development change;
 - 2.3 maternal depressive symptoms change; and
 - 2.4 Concomitant change in parenting, infant social-emotional, and maternal depressive symptom outcomes as a result of intervention.
3. Evaluate moderating influences on parent and infant behavior within the context of depression during the post partum period. We will focus on:
 - 3.1 The extent to which maternal depression prior to intervention, including current depression symptoms as well as depressive history and chronicity, relate to dosage within the MBN program;
 - 3.2 How dosage moderates parent and infant behavioral change as well as maternal depressive symptom change; and

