Statistical Analysis Plan

Title: Reducing Maternal Depression and Promoting Infant Social-Emotional Health & Development

NCT03464630

Date: 09/18/2016

Analytic Strategy

Constructs. We will use a systematic approach to construct development to create two parent outcomes (mother positive/negative) and one infant outcome (infant social emotional functioning). *For our outcomes of maternal depression, parenting knowledge and stress, we will examine single indicants. To view potential intervention moderating effects, we will attempt to create a maternal contextual risk indicant (e.g., isolation/support, relationship status, conflict, economic hardship); for maternal depression prior to intervention as a potential moderator, we will view depression onset, chronicity, and severity as well as presence of other treatment including medication to examine each of these and their effect on intervention outcomes.* For factor analysis, given appropriate internal consistency and inter-rate reliability, we will examine questionnaire scales and observational codes using factor analytic techniques [99], retaining a 5:1 subject to parameter ratio. Scale factor loadings above .30 and communality estimates above .15 will be confirmed within SEM methodology to produce fit indices to view how each indicant set fits into their specified domain. If satisfactory, unit-weighting of the standardized score for each indicant will be summed. If not, we will select an index variable within each domain to represent the outcome.

Random Sampling/Attrition Analysis. Though mother-infant pairs will be randomly assigned to the intervention, condition differences may exist due to random sampling failures or differential attrition. To address this issue, 2×2 (Group x Attrition Status) MANOVAS will be performed using the baseline assessment for mother, infant and contextual risk variables. The presence of a statistically significant Group main effect would provide evidence that random assignment was not effective in equating groups. A second possible source of nonequivalence is differential attrition by condition. A Group x Attrition Status significant interaction provides evidence of differential attrition between groups. In general, analyses will proceed using an “intent to treat” approach and all participants recruited will be included in subsequent analyses.

Examination of Acute Intervention Effects (Aim 2)

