(Aims 2.1 - 2.3) Our post-assessment n, to examine acute intervention effects, is expected to be 150 (75/condition). We will initially view intervention effects on our mother/infant outcomes using a 2 (pre-post) $\times 2$ (MBN intervention group) repeated measure analysis of variance. We will examine the inter-correlations among outcomes and, if significant, will use a MANOVA approach to examining MBN intervention effects. The F test is robust to non-normality if such non-normality is caused by skewness rather than outliers. We will take appropriate measures to reduce outlier influences. **(Aim 2.4)** To examine the relations between mother change (parenting and maternal depression) and infant change, one approach will be to create individual beta estimates for mothers and infant utilizing the polynomial contrast function within MANOVA to produce individual trajectory scores reflecting parent and infant change from pre to post that can then be used in external between-condition covariate analysis. The trajectory scores will be subjected to an analysis of covariance with infant change trajectories as the dependent variable and parent change as the covariate. We will determine whether the parent change covariate is significantly related to the dependent variable (demonstrating that changes in parenting behavior and child functioning covary). We will determine the statistical significance and effect sizes of intervention effects (ignoring the covariate). We will then determine if entering the parent functioning covariate modifies the intervention effect size and statistical significance. If parent change is strongly linked to infant change, then entering the covariate should result in nonsignificant intervention effects. Estimates of covariance-adjusted effect sizes will provide estimates of the proportion of intervention effect size that can be explained by the parenting change variable. We will test for between-group heterogeneity of covariance to determine whether the strength of association between change in parenting and infant functioning differs by intervention group.

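### SAP Aim 2.4 does not say which mother changes form its covariate, yet labels the explained infant effect as parenting, so part of any depression pathway can be credited to parenting

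*SAP*

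**What the plan says.** Protocol, Objective and Specific Aims, Aim 2.4 names three changes to be examined together: "Concomitant change in parenting, infant social-emotional, and maternal depressive symptom outcomes as a result of intervention". The SAP, under Examination of Acute Intervention Effects, opens its Aim 2.4 paragraph in the same spirit: "To examine the relations between mother change (parenting and maternal depression) and infant change".

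The model that follows is an ANCOVA "with infant change trajectories as the dependent variable and parent change as the covariate". From there the mother-side variable goes by several names, and most of the interpretation refers to parenting:

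- A significant covariate is read as "demonstrating that changes in parenting behavior and child functioning covary".
- The next step asks whether "entering the parent functioning covariate modifies the intervention effect size and statistical significance".
- The adjusted effect sizes are to give "the proportion of intervention effect size that can be explained by the parenting change variable".
- The heterogeneity test asks whether "the strength of association between change in parenting and infant functioning differs by intervention group".

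After its opening clause the Aim 2.4 paragraph does not mention depression change again. The Constructs paragraph lists two parent constructs (positive and negative) and treats maternal depression, parenting knowledge and stress as single indicators. It does not say which of these make up parent change. Neither Aim 3 nor Aim 4 gives depression change a covariate of its own or specifies a model with both mother changes.

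**The concern.** The programme is meant to move both maternal depression and parenting, so the two changes may well be correlated within mothers. A model with one mother-side covariate cannot then tell infant benefit that travels with better parenting from infant benefit that travels with relief of depression. The SAP supplies one label for the result, and that label is parenting.

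At stake is the explanatory conclusion of the trial: which change in the mother goes with the infant's gain. The Protocol lists parenting and depressive symptoms separately in Aim 2.4, so a reader will expect an answer for each.

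**Working it through.** The SAP gives no figure for Aim 2.4. Its Power Analysis covers the 2 x 2 analysis only, so there is no figure to reproduce on this point. The check is a worked case.

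**Inputs from the SAP (Power Analysis).** Maternal effects d=.5 to 1.03; infant effect d=.2 to .4; 75 per condition.

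**Assumptions.** P is parenting change and D is depression change, scored so that higher is better, each with within-arm SD 1. The arm differences are dP and dD. The within-arm correlation of P and D is r, which the documents do not give (range shown: 0 to .6). Infant change is I = b·D + error, so depression is the only pathway and the true parenting share is 0%. This is the extreme case.

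**Unadjusted infant effect:** b·dD.

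**Covariate is parenting only.** The within-arm slope of I on P is b·r, so the adjusted effect is b·dD − b·r·dP. The share credited to parenting is r·dP/dD.

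**Covariate is an equal-weight sum P + D.** The within-arm slope is b(1+r)/(2+2r) = b/2 and the arm difference is dP + dD. The share is (dP + dD)/(2·dD), whatever r is.

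| dP | dD | Parenting only, r=0 | r=.2 | r=.4 | r=.6 | Sum P + D |
|---|---|---|---|---|---|---|
| .5 | .5 | 0% | 20% | 40% | 60% | 100% |
| .5 | 1.03 | 0% | 9.7% | 19.4% | 29.1% | 74.3% |
| 1.03 | .5 | 0% | 41.2% | 82.4% | 123.6% | 153% |

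With equal effects the parenting-only share is r itself: 30%, 40% and 50% at r=.3, .4 and .5. A share above 100% means that adjustment reverses the sign of the infant effect.

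**Each variable in its own model.** Depression alone is credited with 100% and parenting alone still with r. At r=.4 and equal effects the two shares add to 140%.

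**Both in one model.** The joint slopes are 0 for P and b for D. Each share is joint slope × arm difference ÷ unadjusted effect: 0·dP/(b·dD) = 0% for parenting and b·dD/(b·dD) = 100% for depression.

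**Each credited only with what it adds over the other.** Parenting gets 0%. Depression gets b(dD − r·dP)/(b·dD) = 1 − r·dP/dD. With equal effects this is 70%, 60% and 50% at r=.3, .4 and .5, where the truth is 100%. This rule under-credits the real pathway.

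**Simulation check** (75 per arm, 4,000 runs, dP=dD=.5, r=.4, b=.4; implied infant effect .4 × .5 = .20, the bottom of the SAP's range). The mean unadjusted effect is .1998. The parenting-only model lowers it by .0796, and .0796/.1998 = 39.8%. The sum covariate explains 99.9%. The joint model gives parenting −0.1% and depression 100%.

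**The case against.** The strongest reply is that the wording is loose rather than wrong. The paragraph defines mother change as both things, speaks of beta estimates and trajectory scores in the plural, and offers the method as one possible approach. With two parent constructs and several single indicators in play, it can be read as a template to be run once per mother variable, with parenting as shorthand. Depression would then have its own ANCOVA. This stands to the extent that the text does not fix the covariate. It does not remove the problem, because separate models still give parenting a share of r·dP/dD.

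A second reply is that the size is not established. The documents do not give r, the share is zero at r=0, and the worked case allows parenting no effect at all. All of that stands, so the percentages are illustrations and not forecasts.

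A third concerns significance. In simulations of this case (dP=dD=.5, r and b each .3 to .5, 75 per arm) the parenting covariate alone is significant in 18% to 88% of trials, against about 5% once depression change is also entered. A reader might infer a false-positive rate of up to 88%. The SAP does not support that reading: it takes significance to mean only that parenting and infant change covary, and in the worked case they do. The misattribution lies in the proportion explained.

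Finally, Protocol Aim 2.4 speaks of concomitant change and not of separating pathways. That is fair to the Protocol, but the SAP itself goes on to a proportion explained and names the variable that explains it.

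**Conclusion.** The point holds in conditional form. The SAP names two mother changes, does not say which enter the model, and has one label for the result. A blended covariate makes the label wrong. A parenting-only covariate, or separate models, credits parenting with part of any depression pathway when the two changes correlate within arm. With depression as the only pathway and equal maternal effects of .5, that part is r; with depression at 1.03 and parenting at .5 it is about half of r (.5/1.03 = .49).

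A reader might infer that infant gains from depression relief will be reported as due to parenting, or that the covariate absorbs the whole depression pathway. The documents do not support either as a certainty. The make-up of parent change is left open, and under a parenting-only covariate the amount runs from nothing upward with a correlation that is not stated.

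This is a cheap improvement to an explanatory sub-aim.

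**What to change.** In the Aim 2.4 paragraph of the SAP:

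- Name parenting change (each parenting construct) and maternal depressive-symptom change as separate covariates.
- Fit the ANCOVA with each alone and with both together.
- Compute each share from the joint model: joint coefficient × between-arm difference in that change ÷ unadjusted infant effect, with bootstrap intervals. Do not rely only on the reduction that each adds over the other.
- Use the name of the variable entered in every result and in the heterogeneity test.
- Word the conclusion as association consistent with a pathway, because the mothers' changes are not randomised.

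The cost is SAP wording and a few more fits on data already planned. The intervals for each share will be wider because the covariates are correlated. The joint model does not settle which change came first or rule out unmeasured common causes.

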Examination of Moderating Influences (Aim 3) Dosage & Skills Acquisition. To evaluate moderating influences on parent and infant behavior our first focus is on how maternal depression prior to intervention (*i.e.*, *chronicity, severity, receipt of psychiatric treatment/medication*) affects MBN intervention dosage (**3.1**); secondly, we are interested in the moderating effect of dosage on mother and infant change (**3.2**). For **3.1**, we will examine a 2 (hi/lo dosage) x 2 (intervention) ANOVA, using maternal depression indicants (*e.g.*, *chronicity*) as the dependent measure. A significant main effect for dosage would indicate that higher levels of maternal depression are found at different dosage levels; it is anticipated that higher depression will be evidenced in the low dosage group. A significant interaction would indicate a higher level of maternal depression is found within a dosage by condition cell. Though we would not anticipate a significant interaction, we will examine if higher levels of depression are associated with low dosage only within the Mom and Baby Net (MBN) intervention group; this could indicate that the skills focus of MBN learning may have been too intense for highly depressed mothers. For **3.2**, examining dosage as a moderating influence on mother and infant change, we will utilize the individual beta-slope estimates reflecting parent and infant change from Aim 2 as the dependent measures in separate 2 (intervention) x 2 (hi/lo dosage) ANOVA designs. We hypothesize a significant interaction term indicating the highest positive change trajectories will be for the intervention mothers with high dosage, when compared to low dosage intervention mothers and Depression and Developmental Awareness (DDAS) mothers regardless of dosage level. If a significant dose-effect relationship exists within the MBN condition, we will determine if an effective dosage level can be identified that is less than the maximum number of intervention sessions offered. **3.3** analysis will examine Pearson correlations between contextual risk and level of maternal depression and a bi-serial correlation for the relation between contextual risk and dosage (hi/lo) to determine if contextual risks are related to both initial levels of depression and subsequent engagement in intervention. To further examine the contextual risk on mother and infant change, we will form a hi/lo risk categorical variable, based on median split, and utilize the same 2 (intervention) x 2 (hi/lo risk). If a main Intervention effect is significant, we would expect MBN mothers and infants, regardless of risk level, to evidence the greatest improvements when compared to DDAS mothers. If significant interaction effects occur, we would expect mothers and infants within the MBN condition with lower levels of risk to evidence the greatest improvement in functioning and, though not statistically significant, that MBN mothers and infants, even in the presence of high risk, would evidence higher positive change trajectories than those of DDAS mothers and infants.

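### The SAP promises to examine whether baseline depression modifies intervention outcomes but gives no model for it, and the lead test for Aim 3.1 pools both arms on an MBN question

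*SAP*

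**What the plan says.** Three statements bear on baseline depression.

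- **SAP, Analytic Strategy, Constructs.** Depression before intervention is listed as a potential moderator. Onset, chronicity, severity and other treatment are to be viewed "to examine each of these and their effect on intervention outcomes".
- **Protocol, Objective and Specific Aims, 3.1.** The aim is how far prior depression (current symptoms, history, chronicity) may "relate to dosage within the MBN program". Dosage is the only response named.
- **SAP, Examination of Moderating Influences (Aim 3), 3.1.** The text begins "our first focus is on how maternal depression prior to intervention" and goes on to its effect on MBN dosage. The model then reverses the roles: "we will examine a 2 (hi/lo dosage) x 2 (intervention) ANOVA, using maternal depression indicants" as the dependent measure. The lead reading is "A significant main effect for dosage would indicate that higher levels of maternal depression are found at different dosage levels". The SAP does not expect an interaction, but adds that "we will examine if higher levels of depression are associated with low dosage only within the Mom and Baby Net (MBN) intervention group".

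The other two parts of Aim 3 use different moderators. Analysis 3.2 is described as "examining dosage as a moderating influence on mother and infant change". Analysis 3.3 concerns contextual risk, where "we will form a hi/lo risk categorical variable, based on median split".

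**The concern.** All mothers in this trial enter with depressive symptoms. Whether benefit depends on how severe or long-standing the depression is, or on treatment already being received, is a natural question, and the SAP says it will look. If no model is written down, the question will go unanswered or be answered by a model chosen after the data are seen.

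Aim 3.1 raises a smaller matter. It is a question about MBN, and the SAP's own worry is that the skills focus of MBN may be too demanding for highly depressed mothers. A main effect averaged over arms is an indirect answer: DDAS mothers contribute half the information. The contrast that would answer directly is mentioned but not specified.

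**Working it through.** **1. Search for the promised moderation test.**

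| SAP analysis | Response | Factor crossed with arm |
|---|---|---|
| Aims 2.1–2.3 | mother and infant outcomes | time |
| Aim 2.4 | infant change | parent change (covariate) |
| 3.1 | baseline depression | dosage |
| 3.2 | mother and infant change | dosage |
| 3.3 | mother and infant change | contextual risk |
| Aim 4 | growth intercept and slope | none (arm as predictor) |

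No row has an outcome as response with baseline depression crossed with arm. Analysis 3.1 cannot stand in, because no post-baseline outcome enters it. A simulation confirms this (4,000 trials, N = 150, true moderation of 0.5 SD per SD of depression, dosage unrelated to depression). The 3.1 ANOVA rejected at the null rate (dosage 5.2%, interaction 4.7%), while a direct arm × depression test rejected in 84%.

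**2. The plan's own power figures.** The SAP gives detectable effects only for the pre-post 2 × 2 analysis (75 per condition, alpha .05). With λ = f² × N × 2/(1 − r), f = d/2 and N = 150:

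- d = .29, r = .21: λ = .145² × 300/.79 = 7.98, power .80
- d = .18, r = .68: λ = .09² × 300/.32 = 7.59, power .78
- d = .37, r = .21: λ = 13.0, power .95
- d = .23, r = .68: λ = 12.4, power .94

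The figures reproduce to rounding. They say nothing about Aim 3, for which no power is stated.

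**3. Precision of the missing test.** For change regressed on arm, continuous baseline depression (in SD units) and their product, 75 per arm, the standard error of the slope difference is √(1/75 + 1/75) = .163 residual SD. At 80% power, two-sided .05: 2.80 × .163 = **.46 SD of change per SD of depression**.

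**4. Does reversing the roles lose the association?** No. In one simulated arm of 75 with hi/lo dosage, a t test of depression by dosage, a linear regression of dosage on depression and the point-biserial correlation all gave p = .1124 (logistic likelihood ratio: .105).

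**5. What pooling and splitting cost.** Inputs from the protocol: 180 dyads allocated 1:1, so 90 per arm. Assumptions: r = .30 between depression and sessions, normal scores, and a median split (the SAP states no dosage cut-off).

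A median split multiplies r by √(2/π) = .798, so .30 becomes .239. The hi/lo difference in depression is then 2 × .239/√(1 − .239²) = .49 SD. Power ≈ Φ(noncentrality − 1.96).

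*Relation in MBN only:*
- Dosage main effect: (.49/2) × √180/2 = 1.65, power 38%
- Dosage × arm interaction: .49/√(4/45) = 1.65, power 38%
- Hi/lo contrast within MBN: .49 × √90/2 = 2.34, power 65%
- Sessions kept continuous, within MBN: atanh(.30) × √87 = 2.89, power 82%

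Simulation (6,000 trials) gives 36–38%, 36–37%, 63–64% and 83%. With 75 per arm the figures are about 31%, 31–33%, 56–57% and 76–77%.

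*Relation in DDAS only:* by symmetry the main effect is significant in about 36–37% of trials, although MBN has no relation.

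*Same relation in both arms:* main effect .49 × √180/2 = 3.31, power 91% (simulation 90%), against 83% for the continuous analysis in MBN alone.

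**The case against.** The case for the plan is substantial on 3.1 and weaker on the missing test.

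- **A reader might infer that 3.1 fails to answer how depression relates to dosage within MBN.** The documents do not support that. The SAP says "we will examine if higher levels of depression are associated with low dosage only within the Mom and Baby Net (MBN) intervention group", and step 4 shows that putting depression on the left-hand side costs nothing when dosage is binary. What stands is narrower: the MBN look has no named contrast. It is also framed as a relation found in MBN and not in DDAS, which is an interaction question and not the MBN association itself.
- **The low power figures belong to a case the SAP does not expect.** It anticipates no interaction, and with a shared relation the pooled test does better than an MBN-only analysis. This is right, and the 36–38% should not be quoted without it. Yet the concern about highly depressed mothers in MBN is the MBN-only case.
- **Much of the gain comes from not splitting dosage.** Within MBN, 63% rises to 83% for that reason alone. The 83% holds for a single predictor. If severity, chronicity and treatment were entered together, with severity correlated .5 and .3 with the other two (an assumption), it would be about 67%.
- **A reader might also fault the SAP for taking indicants one at a time.** Neither document promises to separate their independent effects, so that is a preference and not a defect.
- **The moderation promise is one clause about a potential moderator, and no protocol aim repeats it.** True. The gap is therefore an omission from the SAP against its own Constructs paragraph, not a failure of 3.1 to do its own job.

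**Conclusion.** The concern holds in two limited parts.

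First, the SAP undertakes to examine how baseline depression affects intervention outcomes and specifies no analysis that does so. This follows from reading the plan and rests on no numerical assumption. The missing test would be imprecise (about .46 SD per SD at 80% power with n = 150), so it can only be exploratory.

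Second, 3.1 tests the association it is meant to test, but leads with a result pooled over arms and with dosage split at an unstated point. How much this matters depends on where the relation lies. If it is in MBN only, the planned main effect and interaction each have under half the power of a continuous within-MBN analysis. If it is in DDAS only, the lead test is significant in over a third of trials on an MBN question. If it is equal in both arms, pooling does no harm. These sizes assume r = .30, normal scores and a median split, none of which the documents give.

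This is an inexpensive improvement to secondary aims. It does not touch the main comparison of the arms.

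**What to change.** - **Outcome moderation.** Add to the Aim 2 change model for each outcome an arm × continuous baseline severity term and, in separate models, arm × chronicity and arm × current treatment. Label them exploratory, report estimates with confidence intervals, and state the .46 SD per SD detectable size. Where maternal depression is itself the outcome, interpret only the interaction, since the slope of change on baseline includes regression to the mean.
- **Aim 3.1.** Model the number of sessions completed (the protocol gives 14 in both programs) on each depression indicant, with arm and an arm × indicant term. Report the MBN slope with its confidence interval as the answer to the aim, and the pooled association as secondary. Session counts are bounded and may be skewed, so specify robust standard errors or a count model. If a hi/lo version is kept, state the cut-off in advance and name the within-MBN contrast.

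The cost is SAP wording and a few more models on data the plan already calls for. The interactions will be imprecise, and non-significant ones must not be read as showing that depression makes no difference.

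### Aim 3.3 splits contextual risk at the sample median before testing intervention by risk, which costs power for no stated reason; the within-MBN dose step needs a limit on what may be concluded

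*SAP*

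**What the plan says.** **Contextual risk.** SAP, Examination of Moderating Influences (Aim 3), part 3.3, first treats contextual risk as a score: the analysis "will examine Pearson correlations between contextual risk and level of maternal depression". For the moderator test the plan changes scale: "we will form a hi/lo risk categorical variable, based on median split". The two-level variable enters a 2 (intervention) x 2 (risk) design on mother and infant change. No external cut-point is named, so the median is that of the analysed sample.

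Under Constructs, the SAP says only that it will attempt a contextual risk indicant. Its general scoring rule is that "unit-weighting of the standardized score for each indicant will be summed", which yields a score. The fallback is worded for outcomes: "If not, we will select an index variable within each domain to represent the outcome". Aim 2.4 already plans a test of the ungrouped form, for change in parenting against change in the infant: "We will test for between-group heterogeneity of covariance".

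**Dosage.** Protocol Specific Aim 3.2 is stated as: "How dosage moderates parent and infant behavioral change as well as maternal depressive symptom change". In the SAP, part 3.2 is a 2 x 2 ANOVA of arm by high/low dosage on the change slopes, with no covariate. It continues: "If a significant dose-effect relationship exists within the MBN condition, we will determine if an effective dosage level can be identified", meaning one below the full number of sessions. Part 3.1, on depression and dosage, says "it is anticipated that higher depression will be evidenced in the low dosage group".

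**The concern.** Cutting a score at its median treats a mother just above the cut like the mother at the highest risk, and a mother just below it like the mother at the lowest. Where the underlying relation is graded, information is lost. The Power Analysis section covers the pre-post 2 x 2 analysis and gives nothing for Aim 3, so a moderate intervention-by-risk effect could be missed only because of the split.

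The dose step raises a different issue. Sessions completed are observed after randomization, so comparing high- with low-dosage mothers inside MBN is not a randomized comparison. The SAP itself predicts that the two groups differ in prior depression, and depressive symptom change is one of the 3.2 outcomes. A statement about how many sessions suffice could therefore rest partly on who was more depressed at entry.

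**Working it through.** **The plan's own figures.** Inputs from the SAP Power Analysis: N = 150 (75 per condition), alpha .05, repeated-measures correlation r = .21 or .68. With f = d/2 and m = 2 time points, the noncentrality is f² × N × m / (1 − r), on 1 and 148 df. For d = .29 and r = .21: .145² × 300 / .79 = 7.98, giving power .802. The other stated values give .782 (d = .18, r = .68), .948 (d = .37, r = .21) and .938 (d = .23, r = .68). The SAP figures reproduce to within 2 points, but they concern only the pre-post by group test.

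**Cost of the median split.** Assume a normal risk score with SD 1, residual SD 1 in the change slope, and a linear interaction β. The interaction sizes are assumptions; the documents give none.
- Ungrouped: standard error ≈ 2/√150 = .163, so z = β√150/2.
- Split: a normal score correlates √(2/π) = .798 with its own median split, so z is multiplied by .798.
- Information kept: 2/π = .637. 150 × .637 ≈ 95, so the split is like losing about 54 of the 150 dyads.
- Approximate power = Φ(z − 1.96). Simulated power uses 20,000 trials, least squares, two-sided .05, with error of about a point.

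| β | z ungrouped | z split | Approx. power, ungrouped / split | Simulated power, ungrouped / split |
|---|---|---|---|---|
| .2 | 1.22 | 0.98 | 23% / 16% | 22% / 16% |
| .33 | 2.02 | 1.61 | 52% / 36% | 51% / 35% |
| .465 | 2.85 | 2.27 | 81% / 62% | 79% / 60% |

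With β = 0 both tests reject in about 5% of trials: the split costs power and does not create false positives. With mild skew (.7) it keeps about 61%, and power at .465 is 79% against 58%. With an exponential score it keeps about 48%.

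**Dose step: direction.** With no true dose effect, the high-minus-low difference in improvement equals minus (low-minus-high gap in baseline depression) × (slope of improvement on baseline depression). The gap is an assumption; take .5 SD.
- Depression change, equal pre and post SDs: slope = 1 − r. Bias = −.5 × .79 = −.395 SD (r = .21) or −.5 × .32 = −.16 SD (r = .68). High dosage looks worse.
- An outcome on which more depressed mothers improve less (assumed slope −.3): bias = +.15 SD. High dosage looks better.

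**Dose step: size.** Simulation with n = 75, dosage split at its median, dosage related to measured baseline depression, and no true dose effect. For depression change, the unadjusted test rejects in the wrong direction (nominal 2.5%) in:
- about 4% to 14% of trials at dosage-baseline correlations of −.1 to −.2;
- about 12% to 41% at −.3 to −.4 (12% to 13% and 19% at r = .68; 24% and 41% at r = .21).

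For other outcomes, false findings favouring high dosage run at 3% to 5% if both assumed correlations are .1 to .2, and 9% to 19% if they are .3 to .4.

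**Does adjustment settle it?** In the model above, adding baseline depression returns the two-sided rejection rate to 5%. Now let dosage follow a stable depression level around which the measured score fluctuates, with correlations of −.3 to −.4. The unadjusted test holds 5%, while the adjusted test falsely favours high dosage in about 15% to 24% of trials (r = .68) or 40% to 66% (r = .21). The documents do not say which model applies.

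**The case against.** **Against the split.** The risk composite is only attempted, and its components include relationship status. If a single binary variable stood in for it, there would be nothing to split. An interaction of .465 is large beside the infant effects of d = .2 to .4 that the SAP anticipates, and at .2 the split costs 6 points on a test that would probably fail anyway. Aim 3 is secondary and unpowered. All this stands and limits the weight of the point. It does not supply a reason for the split.

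**Against the dose caution.** The documents give no size for the depression-dosage link, and weak links do little harm. Equal pre and post SDs are also assumed. Eligibility selects on depression screening scores, which may narrow the baseline spread: if the pre SD were .8 of the post SD, wrong-direction rejection at r = .68 and correlations of −.3 to −.4 would be 5% to 7%. The SAP does not say that its r values are for depression. If the step runs only after a significant arm-by-dosage interaction, with similar selection in both arms, false findings fall to about 2%. Masking remains: detection of a true .35 SD dose effect falls from 34% to 19%–24% (r = .68) or 9%–16% (r = .21) at correlations of −.3 to −.4. The SAP does not state whether that condition applies.

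**Stronger readings a reader might infer.**
- That baseline depression is ignored throughout: Constructs lists prior depression as a potential moderator and part 3.1 relates it to dosage. It is absent only from the dose step.
- That the dose step will manufacture a dose effect: for depression change the expected bias runs the other way.
- That a baseline covariate cures the problem: it does so under one selection model and does harm under another.
- That the main trial result is compromised: Aim 2 compares randomized arms and uses neither the split nor dosage. The arm-by-dosage interaction in 3.2 is also much less exposed if selection is similar in both arms.

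**Conclusion.** The point holds, mainly on the median split. Given a roughly normal score and roughly linear moderation, the split discards about 36% of the information. The loss is about 16 to 19 points of power for interactions of .33 to .465 SD, and about 6 points at .2. The direction of the loss is firm under those assumptions; the interaction sizes are illustrative.

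The dose step carries a real but unquantified risk of confounding by baseline depression. Neither the unadjusted nor the baseline-adjusted change analysis is valid under all plausible selection models. What the documents support is a limit on interpretation. They do not support a claim that the step is biased by a known amount or in one direction. This is a change that should be made; it does not threaten the primary comparison.

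**What to change.** **Aim 3.3.** Test arm by continuous contextual risk on the planned change-slope outcome, in the form Aim 2.4 already uses for a continuous covariate. Keep high/low groups for display only. If the composite is not formed and a binary index variable takes its place, use it as it is.

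**Within-MBN dose step.** Report the unadjusted and the baseline-depression-adjusted results side by side, labelled as exploratory associations. Do not conclude from this step that a dosage below the maximum is effective. State whether the step runs only after a significant arm-by-dosage interaction, and define the dosage measure and any cut.

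It may be tempting to report a dose association only where the two results agree in direction. That rule should not be relied on. With no true effect and correlations of −.3 to −.4, it lowers wrong-direction findings on depression change only from about 12%–40% to 12%–33%. In the stable-level model it lowers false findings favouring high dosage only from about 15%–65% to 14%–45%.

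**Cost.** SAP wording only; no new data. Risk results become slopes, which are less simple to present than two groups. If the true risk effect is a step at the sample median (.465 SD either side), the linear test is the weaker one, with 60% power against 81%. The plan proposes no such step.
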